Events NOT meeting UPIRSO criteria:

Events that do NOT meet UPIRSO criteria should be tracked, evaluated, summarized, and submitted to the UTSW HRPP/IRB at continuing review.

For more information on UTSW HRPP/IRB reportable event policy, see <https://www.utsouthwestern.edu/research/research-administration/irb/assets/policies-combined.pdf>.

8.0 DRUG/TREATMENT INFORMATION

N/A (This trial does not use any non-standard or unapproved drug therapy).

9.0 STATISTICAL CONSIDERATIONS

9.1 Study Design/Study Endpoints

- 9.1.1 To decrease the total number of pediatric patients who require general anesthesia compared to historical controls through the use of PROMISE (Primary Outcome).
- 9.1.2 To assess the impact that PROMISE has on patient anxiety and quality of life, treatment time and clinical efficiency, and overall cost.
- 9.1.3 To determine the average patient movement and beam stoppages with PROMISE.

9.2 Sample Size and Accrual

In order to detect a reduction in the rate of general anesthesia use in pediatric patients age 3-7 from the historical control of 70% to the hypothesized 30%, the total number of patients needed to achieve 84% power is 13, using a two-sided exact binomial test with a significance level of 0.05. Over the last two years (2018-2019) at the University of Texas Southwestern we treated 52 pediatric patients aged 3-11 who would be eligible for this study, so on average 26 patients/year. We estimate the ability to enroll the large majority (>80%) of patients who are eligible for this trial, and so we estimate enrolling 20 patients per year. Of these patients, ~42% are ages 3-7, so we estimate that 8-9 patients in our 3-7 age target range per year will be enrolled. Thus, we expect to enroll a total of 30 patients, of whom 13 will be ages 3-7, in ~1.5 years, with the total trial completed in ~2 years.

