| Reference therapy | Institutional historical control of percentage of patients age 3-7 who required general anesthesia during radiation therapy. |
| Statistical Methodology | 
We hypothesize that PROMISE will lead to a reduction in the percentage of patients ages 3-7 who require general anesthesia use from 70% (historical control) to 30%. Using a two-sided exact binomial test with a significance level of 0.05 and power=80%, a sample size of 13 patients (ages 3-7) will be needed to detect this difference.
 
In our past experience, ~42% of children ages 3-11 (eligibility criteria) are between 3-7 years old, so 30 children total will be needed to enroll 13 who are between 3-7 years old.
 |

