1.0 BACKGROUND AND RATIONALE

1.1 Disease Background

Pediatric Radiation Oncology:

Childhood cancers are the leading cause of death in children in the United States. Over 10,000 children are diagnosed annually^{1,2} and, each year, the disease claims more lives than asthma, cystic fibrosis, diabetes, and pediatric AIDS combined. Very little is known about childhood cancer prevention³, and the most common types include leukemias, lymphomas, and central nervous system tumors^{1,2}. Both pediatric cancer incidence and cure rates increased from 1975 to 2004, with cure rates increasing in part because of the advancements in radiation therapy^{1,4}. Some of the innovations that have improved both local tumor control and systemic spread include conformal radiotherapy, brachytherapy, proton beam therapy, and stereotactic radiosurgery⁵. For children with a diagnosis of cancer, radiotherapy is a main curative and palliative treatment modality often administered in combination with surgical resection and/or chemotherapy⁶. While radiation treatments are effective, they are also very intensive. The entire course of radiotherapy for a pediatric patient often consists of 25 to 30 fractions, lasting for 5 to 6 weeks.

General Anesthesia Use in Pediatric Radiation Oncology:

Due to the precise nature of radiation therapy, immobilization is crucial for treatment effectiveness and patient safety^{3,4,7}. For this reason, according to current standard radiotherapy practice most pediatric cancer patients under 7 years of age receive general anesthesia at each fraction to ensure that the patient remains still during the treatment. Almost all children under the age of three, the majority of children under 7, and even some children up to age 12 require general anesthesia⁷. Based on a study by Ntoukas, we estimate 70% of patients age 3-7 can avoid general anesthesia with the implementation of Pediatric Radiation Oncology with Movie Induced Sedation Effect (PROMISE)⁸, which is further described below.

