5.1.3 Demographics

Age, gender, race, ethnicity

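### The primary test compares 13 children aged 3-7 with one pooled 70%, although the protocol says anesthesia need falls with age and nothing controls age within the band

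*Combined protocol and SAP*

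**What the plan says.** **Test.** Section 9.2 sets its sample size "In order to detect a reduction in the rate of general anesthesia use in pediatric patients age 3-7 from the historical control of 70" per cent to 30%. It plans 13 children aged 3-7, "using a two-sided exact binomial test with a significance level of 0.05", and states that "the total number of patients needed to achieve 84% power is 13". The Study Summary gives the same design with 80% power.

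**Comparator.** The Study Summary defines it as "Institutional historical control of percentage of patients age 3-7 who required general anesthesia during radiation therapy". This is one percentage for the whole band. Its denominator, calendar period and age distribution are not given.

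**Age and anesthesia.** Section 1.1 states: "Almost all children under the age of three, the majority of children under 7, and even some children up to age 12 require" general anesthesia. No rate by year of age appears anywhere.

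**Handling of age.** Section 5.1.3 collects it ("Age, gender, race, ethnicity"), but no planned analysis uses it beyond defining the 3-7 band. Section 9.3 describes interim reports only. The design is single-arm.

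**Who enrolls.** Section 3.2.3 lets parents decline. Section 9.2 expects to enroll more than 80% of eligible children, and works with 20 of about 26 a year (20/26 = 77%).

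**The concern.** The protocol itself names age as a predictor of the primary outcome, and a single-arm design has no concurrent group to balance it. The fixed 70% is the right no-effect rate only if the enrolled children come from the same age distribution, within 3-7, as the children behind the 70%.

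If the trial draws systematically older children, for example because families of the youngest decline more often, the no-effect rate falls below 70% and an ineffective system can look successful. If it draws younger children, a real effect is harder to show. As the plan stands, a reader of the final result could not tell whether a low anesthesia count reflects PROMISE or the ages of 13 children.

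**Working it through.** **Inputs.** From section 9.2: n = 13, null 0.70, target 0.30, two-sided alpha 0.05. The age gradients and age mixes in step 4 are assumptions, because the documents give none.

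**1. The plan's own figure.** Let X be the number of the 13 who need anesthesia.
- Lower tail at 0.70: P(X ≤ 5) = 0.0182 and P(X ≤ 6) = 0.0624. The cut-off within 0.025 is therefore X ≤ 5.
- Upper tail: P(X = 13) = 0.70^13 = 0.0097. Total alpha is 0.0182 + 0.0097 = 0.0279.
- Power at 0.30: P(X ≤ 5) = 0.8346, which agrees with the stated 84%. Thirteen is also the smallest n that reaches 80% (n = 11 gives 79.0%, n = 12 gives 72.4%), so the Summary's 80% is compatible. The sample-size arithmetic is sound.

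**2. Shared age distribution.** If each trial child's age is a draw from the historical distribution, each child has a no-effect probability of 0.70 on average over age. X is then binomial(13, 0.70) and the false-positive rate stays at 1.8%, whatever the gradient. Chance imbalance is already inside that figure.

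**3. Shifted distribution, no gradient assumed.** With no PROMISE effect, P(X ≤ 5) for a given true rate in the population enrolled is:

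| True no-effect rate | P(X ≤ 5) |
|---|---|
| 70% | 1.8% |
| 65% | 4.6% |
| 60% | 9.8% |

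**4. What shift could ages produce?** Assume a rate linear in age that averages 70% over ages 3, 4, 5, 6, 7: rate(age) = a + (b − a)(age − 3)/4. Three gradients from age 3 to age 7 are used: 95% to 45%, 85% to 55% and 80% to 60%. For a given set of 13 ages, X is a sum of independent Bernoulli variables with these rates (Poisson-binomial). The cut-off X ≤ 5 is unchanged. Each cell shows the mean no-effect rate, then P(X ≤ 5) with no PROMISE effect.

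| Children aged 3, 4, 5, 6, 7 | Mean age | 95-45% | 85-55% | 80-60% |
|---|---|---|---|---|
| 2, 3, 3, 3, 2 | 5.00 | 70%; 1.2% | 70%; 1.6% | 70%; 1.7% |
| 1, 2, 3, 4, 3 | 5.46 | 64%; 4.2% | 67%; 3.3% | 68%; 2.8% |
| 0, 2, 3, 4, 4 | 5.77 | 60%; 8.4% | 64%; 5.0% | 66%; 3.7% |
| 4, 3, 4, 1, 1 | 4.38 | 78%; 0.1% | 75%; 0.5% | 73%; 0.9% |

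For power in the youngest mix, assume PROMISE multiplies each child's risk by 0.30/0.70. P(X ≤ 5) is then 76%, 79% and 81% for the three gradients, against 83.5% in the plan. With no gradient, no cell would move from 1.8% or 83.5%.

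**5. How unusual are these mixes by chance alone?** If ages were uniform over 3-7, 13 children would have a mean age of at least 5.46 with probability about 14%, at least 5.77 with probability about 3%, and at most 4.38 with probability about 7%.

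**The case against.** The strongest reply is that a fixed historical null is conventional in a single-arm phase II trial, and that the two populations should be alike. The control is institutional, the trial is single-center, PROMISE is proposed for all children aged 3-11 having radiation (section 1.3), and most eligible families are expected to join. That limits selection by age without excluding it: on the plan's own numbers about 6 of 26 eligible children a year are not enrolled, and nothing shows that they resemble the rest in age.

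Several stronger readings are tempting, and the documents do not support them:

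- *Need falls steeply inside 3-7.* Section 1.1 gives a direction in words over wider bands (under 3, under 7, up to 12). The slope within 3-7 is not documented.
- *The test is valid only if the ages match.* A common age distribution is enough (step 2). Only a systematic shift biases the test, and the documents show no evidence of one.
- *The false-positive rate is 8% or 10%.* The 8.4% pairs an age mix at about the 3% point with the steepest assumed gradient. The 9.8% requires a true rate of 60%. Neither is an expected value.
- *The historical group is about 22 children.* That figure is 42% of the 52 patients that section 9.2 cites for accrual. Nothing says the 70% came from them.
- *An exact age-adjusted test should replace the primary test.* It would treat estimated historical rates as known. If the cohort were 22 (an assumption), even the pooled 70% would have a standard error of √(0.70 × 0.30/22) = 9.8 points, and rates by age would be less precise still.

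The omission itself stands: age is a stated predictor, it is collected, and it goes unused.

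**Conclusion.** The concern holds as a gap in the supporting analysis, and does not make the primary test invalid. The direction of the risk follows from the documents: one pooled rate, need that falls with age, and no control of age. Its size does not. It depends on an undocumented gradient and on a shift that may not occur.

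Under the assumed gradients, all six older-mix results exceed the 2.5% lower tail, but only one is clearly above 5%. The loss of power with a younger mix is modest, about 3 to 7 points. It depends on how PROMISE is assumed to act. A constant odds ratio with a more extreme mix (5, 4, 2, 1, 1 children; mean age 4.15) and assumed rates of 85, 80, 70, 60 and 55% gives power of about 57%.

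This is a cheap improvement that would show whether an observed reduction could be an age effect.

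**What to change.** Keep the exact binomial test against 70% as the primary analysis. In section 9.3, pre-specify before outcomes are known:

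1. A table of ages, and of anesthesia use by age, for the historical cohort behind the 70%, with its size and calendar period, next to the ages of the enrolled children aged 3-7.
2. A supporting age-standardised comparison. Assign each enrolled child the historical probability for that child's age, using bands 3-4 and 5-7 or a logistic fit on age. Sum these to an expected number of anesthesia cases and report observed versus expected.
3. An interval or test for that comparison that carries the uncertainty of the historical rates, for example by bootstrapping the historical cohort.
4. A sentence saying that a positive primary result is to be read together with this comparison.

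The cost is one tabulation of existing institutional records and a short addition to section 9.3. No extra patients, visits or data items are needed from the trial. The drawback is imprecise age-specific rates if the historical cohort is small. Smoothing on age or adding earlier years would help, and the interval in item 3 would show what imprecision remains.

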9.3 Data Analyses

Interim Reports: Interim reports will be prepared annually until the results of the study is closed to enrollment. In general, the interim reports will contain information about patient accrual rate with projected completion dates of the trial, as well as other preliminary data as available including PROMISE success rate (i.e. percentage of children enrolled who do not need general anesthesia).

10.0 STUDY MANAGEMENT**10.1 Conflict of Interest**

Any investigator who has a conflict of interest with this study (patent ownership, royalties, or financial gain greater than the minimum allowable by their institution, etc.) must have the conflict reviewed by the UTSW COI Committee and IRB according to UTSW Policy on Conflicts of Interest. All investigators will follow the University conflict of interest policy.

10.2 Institutional Review Board (IRB) Approval and Consent

It is expected that the IRB will have the proper representation and function in accordance with federally mandated regulations. The IRB must approve the consent form and protocol.

In obtaining and documenting informed consent, the investigator should comply with the applicable regulatory requirement(s), and should adhere to Good Clinical Practice (GCP) and to ethical principles that have their origin in the Declaration of Helsinki.

Before recruitment and enrollment onto this study, the subject will be given a full explanation of the study and will be given the opportunity to review the consent form. Each consent form must include all the relevant elements currently required by the FDA Regulations and local or state regulations. Once this essential information has been provided to the subject and the investigator is assured that the subject understands the implications of participating in the study, the subject will be asked to give consent to participate in the study by signing an IRB-approved consent form.

Prior to a patient's participation in the trial, the written informed consent form should be signed and personally dated by the subject and by the person who conducted the informed consent discussion.

10.3 Registration Procedures

All subjects must be registered with the Research Office before enrollment to study. Prior to registration, eligibility criteria must be confirmed with the Research Office Study Coordinator.

New subjects will receive a number beginning with 001 upon study consent such that the first subject consented is numbered 001, the second subject consented receives the number 002, etc.

Upon confirmation of eligibility and enrollment as per the aforementioned instructions, the subject will be assigned a secondary number in the order of enrollment. For example, subject 001 will become 001-01 upon enrollment. If subject 002 screen fails, and subject 003 is the next subject enrolled, subject 003 will become 003-02 and so-on.

Each newly consented subject should be numbered using the schema provided above. Upon registration, the registrar will assign the additional registration/randomization code according to the numbering schema outlined above, which should then be entered as the patient study id in Velos upon updating the status to enrolled.

The numbering schema should clearly identify the site number; the sequential number of the subject enrolled as well as the status of the subjects enrolled so that the number of subjects consented versus the number of subjects actually enrolled may be easily identified.

Subjects that previously enrolled and are receiving subsequent treatments will be eligible at any time, while study is open to enrollment, to continue the study under the same subject number.

10.4 Data Management and Monitoring/Auditing

REDCap is the UTSW SCCC institutional choice for the electronic data capture of case report forms for SCCC Investigator Initiated Trials. REDCap will be used for electronic case report forms in accordance with Simmons Comprehensive Cancer Center requirements, as appropriate for the project

The UTSW Simmons Comprehensive Cancer Center (SCCC) Data Safety Monitoring Committee (DSMC) is responsible for monitoring data quality and patient safety for all UTSW SCCC clinical trials. As part of that responsibility, the DSMC reviews all local serious adverse events and UPIRSOs in real time as they are reported and reviews adverse events on a quarterly basis. The quality assurance activity for the Clinical Research Office provides for periodic auditing of clinical research documents to ensure data integrity and regulatory compliance. A copy of the DSMC plan is available upon request.

Trial monitoring will be conducted according to the study specific monitoring plan. For guidance on creating a monitoring plan, refer to the UTSW SCCC IIT Management Manual.

The SCCC DSMC meets quarterly and conducts annual comprehensive reviews of ongoing clinical trials, for which it serves as the DSMC of record. The QAC works as part of the DSMC to conduct regular audits based on the level of risk. Audit findings are reviewed at the next available DSMC meeting. In this way, frequency of DSMC monitoring is dependent upon the level of risk. Risk level is determined by the DSMC Chairman and a number of factors such as the phase of the study; the type of investigational agent, device or intervention being studied; and monitoring required to ensure the safety of study subjects based on the associated risks of the study. Protocol-specific DSMC plans must be consistent with these principles.

10.5 Adherence to the Protocol

Except for an emergency situation, in which proper care for the protection, safety, and well-being of the study subject requires alternative treatment, the study shall be conducted exactly as described in the approved protocol.

10.5.1 Exceptions (also called single-subject exceptions or single-subject waivers): include any departure from IRB-approved research that is *not due to an emergency* and is:

- intentional on part of the investigator; or
 - in the investigator's control; or
 - not intended as a systemic change (e.g., single-subject exceptions to eligibility [inclusion/exclusion] criteria)
- **Reporting requirement:** Exceptions are non-emergency deviations that require **prospective** IRB approval before being implemented. Call the IRB if your request is urgent. If IRB approval is not obtained beforehand, this

constitutes a major deviation. For eligibility waivers, studies which utilize the SCCC-DSMC as the DSMC of record must also obtain approval from the DSMC prior to submitting to IRB for approval.

10.5.2 Emergency Deviations: include any departure from IRB-approved research that is necessary to:

- Avoid immediate apparent harm, or
- Protect the life or physical well-being of subjects or others
 - **Reporting requirement:** Emergency deviations must be promptly reported to the IRB within 5 working days of occurrence.

10.5.3 Serious Noncompliance (formerly called **major deviations** or **violations**): include any departure from IRB-approved research that:

- Increase risk of harm to subjects; and/or
- Adversely affects the rights, safety, or welfare of subjects (any of which may also be an unanticipated problem); and/or
- Adversely affects the integrity of the data and research (i.e., substantially compromises the integrity, reliability, or validity of the research)
 - **Reporting requirement*:** Serious Noncompliance must be promptly reported to the IRB within 5 working days of discovery.

10.5.4 Continuing Noncompliance: includes a pattern of repeated noncompliance (in or more protocols simultaneously, or over a period of time) which continues **after** initial discovery, including inadequate efforts to take or implement corrective or preventive action within a reasonable time frame.

➤ **Reporting requirement*:** Continuing Noncompliance must be promptly reported to the IRB within 5 working days of discovery.

10.5.5 Noncompliance (that is neither serious nor continuing; formerly called minor deviations) any departure from IRB-approved research that:

- Does not meet the definition of serious noncompliance or continuing noncompliance
 - **Reporting requirement*:** Noncompliance that is neither serious nor continuing should be tracked and summarized the next IRB continuing review, or the notice of study closure- whichever comes first..

*Reporting Requirements reflect UTSW HRPP/IRB guidelines; participating sites should follow the reporting guidelines for their IRB of record

10.6 Amendments to the Protocol

Should amendments to the protocol be required, the amendments will be originated and documented by the Principal Investigator. A summary of changes document outlining proposed changes as well as rationale for changes, when appropriate, is highly recommended. When an amendment to the protocol substantially alters the study design or the potential risk to the patient, a revised consent form might be required.

The written amendment, and if required the amended consent form, must be sent to the IRB for approval prior to implementation.

10.7 Record Retention

Study documentation includes all Case Report Forms, data correction forms or queries, source documents, Sponsor-Investigator correspondence, monitoring logs/letters, and

regulatory documents (e.g., protocol and amendments, IRB correspondence and approval, signed patient consent forms).

Source documents include all recordings of observations or notations of clinical activities and all reports and records necessary for the evaluation and reconstruction of the clinical research study.

Government agency regulations and directives require that the study investigator retain all study documentation pertaining to the conduct of a clinical trial. In the case of a study with a drug seeking regulatory approval and marketing, these documents shall be retained for at least two years after the last approval of marketing application in an International Conference on Harmonization (ICH) region. In all other cases, study documents should be kept on file until three years after the completion and final study report of this investigational study.

10.8 Obligations of Investigators

The Principal Investigator is responsible for the conduct of the clinical trial at the site in accordance with Title 21 of the Code of Federal Regulations and/or the Declaration of Helsinki. The Principal Investigator is responsible for personally overseeing the treatment of all study patients. The Principal Investigator must assure that all study site personnel, including sub-investigators and other study staff members, adhere to the study protocol and all FDA/GCP/NCI regulations and guidelines regarding clinical trials both during and after study completion.

The Principal Investigator at each institution or site will be responsible for assuring that all the required data will be collected and entered onto the Case Report Forms. Periodically, monitoring visits may be conducted and the Principal Investigator will provide access to his/her original records to permit verification of proper entry of data. At the completion of the study, all case report forms will be reviewed by the Principal Investigator and will require his/her final signature to verify the accuracy of the data.

